8.8.3 Analyses of Exploratory Efficacy Endpoints

An ANCOVA model with period baseline as a covariate, treatment sequence, treatment group, period as fixed effects, and a random effect for subject within the sequence, will be used to analyze change from period baseline to treatment week 10 in performance score and change from period baseline to treatment week 10 in satisfaction score as assessed by COPM.

An ANCOVA model with study baseline as a covariate, treatment sequence, treatment group, period as fixed effects, and a random effect for subject within the sequence, will be used to analyze the following other efficacy endpoints:

- Physician CGI-I score at treatment week 10, the Physician CGI-S study baseline will be used as an explanatory variable
- Physician CGI-S score at treatment week 10, the Physician CGI-S period baseline will be used as an explanatory variable
- Change from study baseline to treatment week 10 in mean daytime activity, mean nighttime activity, and percent time in moderate or higher intensity activity as measured by a wrist-worn actigraphy device at select study sites where feasible

Frequency, mean duration and total duration of disabling paroxysmal movement disorder events over time throughout the three-year OLE period will be summarized. Change from

study baseline in percentage of movement disorder free days during the three-year OLE period will also be summarized.

Efficacy Endpoints during the three-year OLE period including 12MWT, Patient/caregiver CGI-I, CANTAB, Physician CGI-I, Physician CGI-S, performance score and satisfaction score as assessed by COPM, PROMIS scores (domain scores) will be summarized and study baseline will be used.

8.9 Safety Analyses

All safety analyses will be performed using the Safety Analysis Set. Safety parameters will include AEs, clinical laboratory parameters, vital signs, ECG parameters, and other safety parameters. No statistical comparisons will be performed.

8.9.1 Adverse Events

Adverse events will be coded by SOC and PT using the Medical Dictionary for Regulatory Activities (MedDRA). AEs during Run-In period will be summarized.

A treatment emergent adverse event (TEAE) will be considered and assigned to the treatment group (UX007 or Placebo) if the AE (classified by preferred term) start date occurs or worsens in severity on or after the first dose of study drug in the corresponding treatment period and before the first dose of study drug in the next treatment period. For example, an AE will be assigned to the treatment in Treatment Period I if it occurred during the wash out period. An AE that occurs within 30 days after the last dose of study drug in the last treatment period will be assigned to the last treatment period.

The incidence of subjects reporting TEAEs in each treatment and treatment sequence will be tabulated by SOC and PT; by SOC, PT, and severity; and by SOC, PT, and relationship to study drug. If more than one event occurs with the same preferred term for the same subject, the subject will be counted only once for that preferred term using the most severe and most related occurrence for the summarizations by severity and by relationship to the study drug.

The incidence of subjects reporting TEAEs by treatment and treatment period will also be summarized by SOC and PT for each of the following categories:

- All TEAEs
- Treatment related TEAEs
- Grade 3 or 4 TEAEs
- Serious TEAEs
- Serious and related TEAEs
- TEAEs leading to study discontinuation
- TEAEs leading to treatment discontinuation

- TEAEs leading to death

Exposure adjusted TEAE incidence is defined as total number of occurrences of an event summed across all subjects by treatment divided by the total exposure duration. A TEAE which occurred during the wash-out period will be considered and counted into the first treatment period. Exposure adjusted TEAE incidence will be summarize by treatment, and period.

Detailed listings for all AEs, TEAEs, serious TEAEs, AEs leading to study/treatment discontinuation, and death will also be generated.

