In a recent, open-label Phase 2 study, paroxysmal manifestations improved significantly ( $p=0.028$ ) in six evaluable patients, in response to treatment with triheptanoin (Mochel et al. 2015). Subjects were asked to record all paroxysmal non-epileptic manifestations including motor (e.g., hyperkinetic movement disorders, speech disorder, and limb weakness) and non-motor (e.g. fatigue, headache, sleep disturbance, disorientation, and mood disorder) events prior to and post treatment with triheptanoin. The numbers of motor and non-motor events were markedly reduced during treatment with triheptanoin followed by an increase in these paroxysmal events when triheptanoin treatment was subsequently withdrawn. Subjects were also asked to score changes in their clinical condition since the start of triheptanoin therapy. Patient-reported clinical global impression of improvement (CGI-I) scores demonstrated a clear improvement after the triheptanoin treatment period followed by worsening of their condition on withdrawal of treatment, tracking the temporal profile of changes in frequency of paroxysmal manifestations. Physicians also rated the severity of the study subjects based on their clinical experience with Glut1 DS and considered these subjects, in whom paroxysmal events were the primary manifestation of the disease, to be moderately to markedly ill. The most common motor manifestations included muscle stiffness, movement disorder, and weakness. All of these symptoms decreased in frequency when treatment with triheptanoin was initiated. During Baseline in the Mochel study, functional  $^{31}\text{P}$ -nuclear magnetic resonance spectroscopy (f-MRS) showed no change in Pi/PCr ratio during brain activation in the Non KD population. After the UX007 treatment period, the bioenergetics profile normalized; repeated measures ANOVA ( $p= 0.014$ ), with an increase in Pi/PCr ratio during visual stimulation and a significant decrease during recovery ( $p= 0.021$ ). Increased Pi/PCr ratio during brain activation reflected a proportional elevation of ADP, allowing increased mitochondrial ATP production with UX007. After treatment withdrawal, the f-MRS profile reverted to the baseline levels (Mochel et al. 2015). These data suggest that UX007 improves energy availability for brain function.

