Actigraphy 		X			X				X
SPECIALTY LABORATORY ASSESSMENTS									
UX007 Metabolites 			X		X		X		X
BHB for ketosis detection	X		X		X		X		X
TREATMENT & DIETARY ASSESSMENTS									
Dietary Assessment and Consultation & Training on 3-day Diet Diary	X								
Dietary Assessment & Review of 3-day Diet Diary			X		X		X		X
Dietitian Consultation			X	X	X		X	X	X
Daily Study Medication Diary 			X	X	X		X	X	X
Review of Study Medication Diary			X	X	X		X	X	X
Daily Treatment with IP/Placebo			X	X	X		X	X	X

ASSESSMENT	Screening Visit Week -6	6-week Run-in Period	TREATMENT PERIOD 1			2-week Washout	TREATMENT PERIOD 2		
			Baseline 1	Phone Visits 1, 2, and 3	End of Treatment 1		Baseline 2 (End of Washout)	Phone Visits 4, 5, and 6	End of Treatment 2
			Week 0 (± 3 days)	Weeks 2, 4, and 6 (± 3 days)	Week 10 (± 3 days)		Week 12 ±3 days	Weeks 14, 16, and 18 (± 3 days)	Week 22 (± 3 days)
Dispense Study Drug			X				X		X 
Treatment Compliance & Accountability				X	X			X	X

1 Suicidal ideation and behavior will be assessed in subjects who are ≥ 10 years of age at each visit

2 For subjects ≥ 18 years old, lipid profile blood tests (LDL, HDL, total cholesterol, and triglycerides) will be assessed at Baseline 1 (Week 0), End of Treatment 1 (Week 10), and End of Treatment 2 (Week 22) after an overnight fast (8-12 hours).

3 For females of child-bearing potential

4 Plasma metabolite samples will be collected at time of SAE, if feasible

5 The definition of an AE also encompasses any increases in frequency or severity, or changes in type of Glut1 DS-associated symptoms, including but not limited to seizures, movement disorders, behavioral abnormalities, cognitive function, etc.

6 Glut1 DS symptom diary and study medication diary will be completed daily by the patient/caregiver. Review of the daily diaries will be performed at clinic or phone visits as indicated (or more frequently if needed)

7 CANTAB will be performed at select study sites

8 An actigraphy device will be worn on the last 10 days of the Run-in Period, the last 10 days of Treatment Period 1, and the last 10 days of Treatment Period 2 at select study sites, where feasible. Training for the actigraphy device will be provided at the Screening Visit.

9 Blood for plasma at Baseline Visits will be collected pre-dose. Blood for plasma at End of Treatment visits 1 and 2 will be collected approximately 90 minutes post dose.

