#### **7.5.4.10 Adverse Events**

All AEs will be recorded from the time the subject signs the informed consent through 30 days following the last administration of study drug. The determination, evaluation, reporting, and follow-up of AEs will be performed as outlined in Section 8.5. At each visit subjects will be asked about any new or ongoing AEs since the previous visit. Assessments of AEs will occur at each study visit.

Clinically significant changes in vital signs, clinical laboratory, or ECG parameters will be recorded as AEs or SAEs, if appropriate, as well as any increases in frequency or severity or changes in type of Glut1 DS associated symptoms (including but not limited to seizures, movement disorders, behavioral abnormalities, cognitive function, etc.).

A blood sample will be collected for UX007 metabolite concentrations in the event of an SAE, if feasible.

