### 8.5.4 Adverse Event Reporting

#### 8.5.4.1 General

All AEs (i.e. any new or worsening in severity or frequency of a preexisting condition) with onset after the subject signs consent for study participation must be promptly documented on the CRF. The Investigator is responsible for evaluating all AEs, obtaining supporting documents, and ensuring documentation of the event is adequate. Details of the AE must include severity, relationship to study drug, duration, and outcome.

All AEs will be collected from the time the subject signs informed consent through 30 days following the last dose of study drug. In addition, the Investigator should report any AE that occurs after this time period that is believed to have a reasonable possibility of being associated with study drug.

AEs ongoing at 30 days following the last dose of study drug should have a comment in the source document by the Investigator whether the event has recovered, recovered with sequelae, or stabilized.

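### SAP 8.9.1 assigns washout-onset AEs to the Period I treatment, so symptom return after UX007 is stopped may be counted as a UX007 TEAE with no display that separates it

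*SAP*

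**What the plan says.** Protocol 7.5.4.10 requires recording as AEs of "any increases in frequency or severity or changes in type of Glut1 DS associated symptoms", and names seizures and movement disorders among them. A footnote to Table 2.2 repeats this: "The definition of an AE also encompasses any increases in frequency or severity, or changes in type of Glut1 DS-associated symptoms". Protocol 8.5.4.1 describes AEs as "any new or worsening in severity or frequency of a preexisting condition". None of these places gives a reference level for the increase. Table 2.2 marks AE collection in the washout column.

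SAP 8.9.1 assigns an AE to a treatment by the date on which it begins or becomes more severe. The qualifying window is "on or after the first dose of study drug in the corresponding treatment period and before the first dose of study drug in the next" period. The SAP spells out the consequence: "an AE will be assigned to the treatment in Treatment Period I if it occurred during the wash out period". After the last treatment period, AEs within 30 days of the last dose go to that period. For exposure-adjusted incidence the SAP adds: "A TEAE which occurred during the wash-out period will be considered and counted into the first treatment period". SAP 5.3 measures exposure from first to last dose within each period, so washout is not in the denominator.

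Protocol 7.6.3.3 is narrower. It treats as treatment-emergent the AEs that begin while the subject is on treatment.

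On what to expect after stopping, the protocol synopsis says of the earlier open-label study that paroxysmal events fell on triheptanoin, "followed by an increase in these paroxysmal events when triheptanoin treatment was subsequently withdrawn".

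**The concern.** Carrying washout events back to the preceding treatment is a common cautious rule. It is neutral between treatments when the background event rate does not change at the last dose. Here it may change: an effective drug for a chronic disease is stopped, the disease symptoms may return, and an increase in those symptoms is itself an AE. Stopping placebo in Period I takes no benefit away.

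The UX007 column of the TEAE tables could therefore mix events that arise on UX007 with loss of its effect after it is stopped, and no planned table tells them apart. The by-period tables fold washout into Period I, and the by-sequence tables do not split by onset relative to the last dose. Only the listings would allow a reader to separate the two. These tables are the planned description of UX007 safety against placebo, so each column should have a clear meaning.

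**Working it through.** The documents give no figure for AEs in washout and no rate at which symptom return would be recorded. The working therefore traces where events are counted, then shows a range under stated assumptions.

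**Where symptom return is counted**
- UX007/placebo, onset in washout: UX007.
- UX007/placebo, onset after the first Period II placebo dose: placebo.
- UX007/placebo, onset in washout and continuing into Period II: UX007, and also placebo only if severity worsens there.
- Placebo/UX007, any AE with onset in washout: placebo, with no loss of UX007 benefit involved.
- Placebo/UX007, stopping after Period II without entering the extension, onset within 30 days of the last dose: UX007.
- Placebo/UX007, entering the extension: UX007 continues, so there is no withdrawal at that point.

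**Crude incidence**
Inputs: 20 subjects per sequence and 40 in total (SAP 3.6). In a completed crossover all 40 receive UX007. Let p be the share of the 20 UX007-first subjects who have a disease-worsening AE only in washout. This p is assumed. Subjects who already had the same preferred term on UX007 add nothing, because each subject counts once per term.

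Rise in UX007 incidence = 20p / 40.
- p = 10%: 2/40 = 5 percentage points.
- p = 25%: 5/40 = 12.5 percentage points.

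With the planned 15% discontinuation applied equally to both sequences, 17 of 34 replaces 20 of 40 and the percentages do not change.

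**Exposure-adjusted incidence**
Inputs: a 10-week Period I and a 2-week washout (SAP 3.1), with exposure as in SAP 5.3.
- Period I: the numerator window is 70 + 14 = 84 days and the denominator is 70 days. Ratio 84/70 = 1.20.
- Each treatment pooled over both periods: (20 × 84 + 20 × 70) / (40 × 70) = 1.10, leaving aside the 30-day rule after Period II.

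This inflation is the same for UX007 and placebo if the event rate is constant. The withdrawal component comes on top and falls on UX007. Planned UX007 exposure is 40 × 70 / 365.25 = 7.67 person-years. With one event per affected subject, p = 10% adds 2/7.67 = 0.26 per person-year and p = 25% adds 5/7.67 = 0.65.

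**After the change**
With onset limited to first through last dose, the Period I ratio is 70/70 = 1.00. Washout-only cases add nothing to the on-treatment UX007 column and appear in their own column instead.

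**The case against.** The strongest case against is that recording is not assured. Read against study baseline, a subject who returns to the enrolled event rate has not worsened, and only a rebound above that rate would be an AE. The protocol's wording is broad enough for the on-treatment reading but does not require it. This stands, so the point is that symptom return may be counted, not that it must be.

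A reader might go further and infer that up to 20 of 40 UX007 subjects (50%) would carry such a TEAE, since the planned means of 8 and 4 events per 4 weeks imply a doubling on return. The documents do not support that. SAP 3.6 gives a mean difference of 4 with a standard deviation of the difference of 7.4. Under normality the share with any benefit to lose is Φ(4/7.4), about 0.71, or roughly 14 of 20. The washout is also only 2 weeks, so full return at the planned means is about 4 events against 2.

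A reader might also infer that the distortion runs in one direction only. It does not: symptom return that starts after the first Period II placebo dose is counted for placebo, over a 10-week window.

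Other points carry weight. A TEAE is defined by timing and is not a finding of toxicity, and investigators may rate these events unrelated. Tables by relationship, sequence and period are planned, and an excess in the UX007 Period I cell over the UX007 Period II cell could be a hint. SAP 8.9 plans no statistical comparisons. Amendment 2 added disease worsening to the AE definition deliberately, after regulatory feedback. The evidence for worsening on withdrawal is six evaluable patients in an open-label study that counted motor and non-motor events.

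These points limit the consequence but do not remove the gap. The all-TEAE, serious and Grade 3 or 4 tables would still place such events under UX007, and no planned table labels them as off-drug.

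**Conclusion.** The point holds as a limited, inexpensive improvement to the safety displays. Under SAP 8.9.1, disease symptoms that return in washout after UX007 may be counted as UX007 TEAEs, and the Period I placebo stop has no counterpart. Subjects who stop UX007 after Period II without entering the extension are affected in the same way through the 30-day rule. Later return, during Period II placebo, goes to placebo, so the net effect on the comparison cannot be signed from the documents alone.

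The size is unknown. The 5 and 12.5 points rest on assumed shares of 10% and 25% with a washout-only AE, and on sites judging an increase against the on-treatment state or recording a rebound above baseline. Two findings need no such assumption. The SAP attribution window is wider than the treatment-emergent definition in Protocol 7.6.3.3. Exposure-adjusted incidence also uses mismatched windows, with a planned Period I ratio of 1.20. No efficacy estimate, test or error rate is affected.

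**What to change.** In SAP 8.9.1:
- Keep the all-TEAE table as planned.
- Add a UX007 versus placebo incidence table limited to onset from first to last dose of each period.
- Show TEAEs with onset in washout, or after the last dose, in a separate column by preceding treatment, with Glut1 DS symptom worsening identified.
- Use the same window for the numerator and denominator of exposure-adjusted incidence.
- Reconcile the SAP definition of treatment-emergent with Protocol 7.6.3.3.

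The split is useful whichever reference level sites applied, and it makes any worsening after withdrawal visible. Onset and dose dates are already needed for SAP 8.9.1 and 5.3. The cost is SAP wording and one extra table split, and no safety information is removed.

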5.3 Duration of Exposure

- Duration of exposure to Investigational Product (IP) (Placebo or UX007), in days, is defined as:
 - During the DB Treatment Period: defined as last dose date of IP in the corresponding treatment period of the DB Period – first dose date of IP in the corresponding treatment period of the DB Period + 1 day
- Duration of exposure to UX007, in days, is defined as:
 - During the OLE Period is defined as last dose date of UX007 in OLE Period – first dose date of UX007 in OLE Period + 1 day
 - During the whole study is defined as the sum of the duration of exposure to UX007 in days during the DB Treatment Period and the duration of exposure to UX007 in days during the OLE Period

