7.3 Visit Time Windows

[Table 1](#) presents the assigned target study day and study day window for each study period. Movement disorder frequency and duration recorded on diary will be mapped to specified period according to [Table 1](#) and actual visit days. For other scheduled efficacy and safety assessments the visit window assigned and the corresponding target treatment days during which an actual visit may occur is specified in [Table 2](#).

Table 1: Visit Mapping Window for Movement Disorder Diary

Period		Planned Duration	Target Study Day	Study Day Window
Run-In		6 weeks	[-42, 0]	<1
DB Treatment Period I	Titration	2 weeks	[1,15]	[1, 15]
	Maintenance	8 weeks	[16,71]	For subjects who entered into washout period: [study day of first dose in Treatment Period I+15, the end of Treatment Period I]; For subjects who did not enter into washout period: \geq study day of first dose in Treatment Period I+15
Washout		2 weeks	[72,85]	For subjects who entered into Treatment Period II ^[1] : [the end of Treatment Period I+1, study day of first dose in Treatment Period II-1]; For subjects who did not enter into Treatment Period II: \geq the end of Treatment Period I +1
DB Treatment Period II	Titration	2 weeks	[86,99]	[study day of first dose in Treatment Period II, study day of first dose in Treatment Period II+14]
	Maintenance	8 weeks	[100,155]	For subjects who entered into extension period: [study day of first dose in Treatment Period II+15, the end of Treatment Period II]; For subjects who did not enter into OLE period: \geq study day of first dose in Treatment Period II+15
OLE Period	Week 34	12 weeks	[156, 281]	[study day of first OLE dose date, 281]
	Week 46	12 weeks	[282,365]	[282,365]
	Week 58	12 weeks	[366, 449]	[366, 449]
	Week 70	12 weeks	[450, 533]	[450, 533]
	Week 82	12 weeks	[534, 617]	[534, 617]
	Week 94	12 weeks	[618, 701]	[618, 701]
	Week 106	12 weeks	[702, 785]	[702, 785]
	Week 118	12 weeks	[786, 869]	[786, 869]
	Week 130	12 weeks	[870, 953]	[870, 953]
	Week 142	12 weeks	[954, 1037]	[954, 1037]
	Week 154	12 weeks	[1038, 1121]	[1038, 1121]
	Week 166	12 weeks	[1122, 1205]	[1122, 1205]
	Week 178	12 weeks	\geq 1206	\geq 1206

[1] Enter into treatment Period II is defined as subjects having taken any Treatment Period II dosing

[2] Enter into OLE phase is defined as subjects having taken any OLE phase dosing.

Table 2: Visit Window for Other Scheduled Efficacy and Safety Assessments

Period	Study Week	Treatment Week	Target Day	Study Day Window

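### The exposure-adjusted TEAE rate counts washout and post-dose events but divides only by first-to-last-dose days, which raises the Period I rate by a factor of 1.20

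*SAP*

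**What the plan says.** SAP 8.9.1 assigns a TEAE to a treatment if it starts or worsens on or after the first dose in a period and "before the first dose of study drug in the next treatment period". Two further rules extend the count past the last dose:

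- Washout, stated directly after the rate is defined: "A TEAE which occurred during the wash-out period will be considered and counted into the first treatment period".
- Follow-up: "An AE that occurs within 30 days after the last dose of study drug in the last treatment period will be assigned" to that last period.

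The rate is the "total number of occurrences of an event summed across all subjects by treatment divided by the total exposure duration", and "Exposure adjusted TEAE incidence will be summarize by treatment, and period".

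SAP 8.9.1 does not define the denominator. The only definition is in SAP 5.3. For a double-blind period it takes the "last dose date of IP in the corresponding treatment period of the DB Period", subtracts the first dose date in that period and adds 1 day. For UX007 over the whole study: "During the whole study is defined as the sum of the duration of exposure to UX007 in days during the DB Treatment Period" and the corresponding extension days. None of these durations includes washout or post-dose days.

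Protocol 7.6.3.3 asks for AE numbers and rates over study-drug exposure in the double-blind part, and over the whole study including the open-label part. It sets no event window and leaves the detail to the SAP.

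**The concern.** A rate per unit of exposure needs events and time taken from the same days. Here the numerator covers first dose to the end of the TEAE window, and the denominator covers first dose to last dose. Every event that starts in the gap is counted against no time.

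The gap differs between the periods. Period I is followed by a two-week washout. Period II is followed by the extension without a planned break, or by 30 days of follow-up if the subject does not continue. A subject with a constant event rate would therefore show different printed rates in the two periods. A reader of the by-period table could take that for a change in tolerability over time. The absolute rates would also be too high as rates per day at risk.

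**Working it through.** The documents give no value for this rate, so there is no figure to reproduce. The event count is the same whichever denominator is used, so the distortion against a matched denominator is

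factor = (days over which events are counted) / (days in the SAP 5.3 duration).

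This holds whatever the event rate off drug.

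**Inputs**
- Treatment Periods I and II: 10 weeks = 70 days each; washout: 2 weeks = 14 days (SAP 3.1). Check: 10 + 2 + 10 = 22 weeks, and 6 + 22 = 28 weeks, as in SAP 3.3.
- Post-dose window: 30 days (SAP 8.9.1).
- Planned gap between Period II and the extension: 0 days, because UX007 is dispensed at Week 22 (protocol 7.4).

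**Per completer, planned schedule**
- Period I, then starts Period II: (70 + 14)/70 = 84/70 = 1.20.
- Period II, enters the extension (read as the next treatment period): 70/70 = 1.00. A 3-day gap before the first extension dose would give 73/70 = 1.04.
- Period II, does not enter the extension: (70 + 30)/70 = 100/70 = 1.43.

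**Sensitivity of the Period I factor**
- SAP Table 1 target days (71 on treatment, 14 in washout): 85/71 = 1.20.
- Week 10 three days late and Week 12 three days early: 81/73 = 1.11. The reverse: 87/67 = 1.30.

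**Against the on-drug rate.** Let r be the washout event rate divided by the on-drug event rate. The documents do not give r. The Period I factor is (70 + 14r)/70 = 1 + 0.2r, which is 1.00, 1.10, 1.20 and 1.40 at assumed r of 0, 0.5, 1 and 2.

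**Pooled by treatment.** With balanced sequences, no dropout and full extension entry, each treatment has (84 + 70)/140 = 1.10, so the UX007-to-placebo ratio is 1.00. Against the on-drug rate this also needs the same r after both treatments.

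The cases below use assumed inputs, with 20 subjects per sequence where numbers of subjects matter. They show only the order of magnitude:
- Five UX007 and one placebo dropout at Day 20 of Period I, all others completing and entering the extension. UX007: (15×84 + 5×50 + 19×70)/(15×70 + 5×20 + 19×70) = 2840/2480 = 1.145. Placebo: (19×84 + 50 + 15×70)/(19×70 + 20 + 15×70) = 2696/2400 = 1.123. Ratio 1.02.
- Four of 20 in the placebo/UX007 sequence not entering the extension. UX007: (20×84 + 20×70 + 4×30)/2800 = 3200/2800 = 1.143, against 1.100 for placebo. Ratio 1.04; with the other sequence affected instead, 0.96.
- UX007 pooled over a full extension (Week 22 to Week 178 = 156 weeks = 1092 days) plus 30 days, one subject per sequence: (154 + 2×1122)/(140 + 2×1092) = 2398/2324 = 1.03, against 1.10. Ratio 0.94.
- Different r, against the on-drug rate, pooled factor (140 + 14r)/140. With r = 2 after UX007 and 1 after placebo: 1.20/1.10 = 1.09. With r = 0 and 1: 1.00/1.10 = 0.91.

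**The case against.** The strongest defence has three parts. First, giving washout events to the preceding treatment is a deliberate convention that SAP 8.9.1 states twice. Second, no safety objective compares periods, and SAP 8.9 excludes statistical comparisons. Within one period both treatments follow the same window rule, so for completers with equal r the factor cancels between arms. Third, if few events start off drug, the excess over the on-drug rate is small.

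The first part stands as a defence of the assignment, but not of a denominator that ignores it. The second stands and limits the severity. It does not remove the by-period difference, because the SAP asks for the rate by period. The third cannot be settled, because r is not given. The protocol synopsis reports that paroxysmal events rose after triheptanoin was withdrawn in an open-label study with six evaluable patients, and protocol 7.5.4.10 records increases in such symptoms as AEs. The rise reported is from on-treatment levels; the synopsis does not say that it went above the pre-treatment level. That makes an off-drug excess possible, not established.

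A reader might also infer that the extension is not a treatment period, because SAP 7.3 names it differently ("Enter into OLE phase is defined as subjects having taken any OLE phase dosing"). Period II would then be the last treatment period for everyone. Extension entrants would carry 100/70 = 1.43, the pooled factor would be (84 + 100)/140 = 1.31, the direction against Period I would reverse, and early open-label UX007 events in the UX007/placebo sequence would go to placebo. The documents do not support this as an equal reading. The SAP usually adds a double-blind qualifier when it means only those periods (5.3, 5.5), and 8.9.1 does not. SAP 5.3 also defines UX007 exposure in the extension. On that reading, extension AEs starting more than 30 days after Period II would have no TEAE assignment, although protocol 7.6.3.3 calls for summaries that include the open-label part. The SAP does not state the workable reading in a sentence, so a clarification is reasonable.

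**Conclusion.** The point holds and is minor. As written, the formula mismatches numerator and denominator. The printed rate is 1.20 times the rate per day at risk for a Period I completer who starts Period II, 1.00 for a Period II completer who enters the extension, and 1.43 for one who does not. These figures assume planned durations, no gap before the extension, and that the exposure duration in 8.9.1 is the one defined in 5.3; 8.9.1 does not refer to 5.3, but no other definition exists.

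A reader might infer that the rate is biased between UX007 and placebo. The documents do not show this. The pooled ratio is 1.00 with no dropout, full extension entry and equal off-drug event rates. In the assumed cases above it stays between 0.91 and 1.09, and none of their inputs for dropout, extension entry or r comes from the documents. No hypothesis test and no subject-incidence table is affected.

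**What to change.** Use one window for events and time, by either of two options.

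(a) Keep the stated assignment of events. Divide by the days from first dose to the end of the TEAE window, which is the day before the first dose of the next period (including the extension), or last dose plus 30 days or end of follow-up. Label the result a time-at-risk rate. This changes only the denominator. The drawback, if no events start off drug, is dilution of the on-drug rate: 17% in Period I (70/84 = 0.83), 30% for a Period II completer who does not enter the extension (70/100), and more for early dropouts, for example 60% for a Day 20 dropout (20/50).

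(b) Count only TEAEs that start or worsen from first to last dose in the period, and divide by the SAP 5.3 duration. Report washout and follow-up events separately by preceding treatment. This is closer to the protocol 7.6.3.3 wording on exposure. The drawback is that the rate's event set then differs from the TEAE incidence tables and from the SAP's washout assignment.

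As a clarification only, state that the extension counts as the next treatment period and that the last treatment period is the last one the subject entered.

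The cost is two SAP sentences and one derived variable (a time-at-risk duration or an on-drug onset flag) from data already collected. Option (b) adds one table line for washout and follow-up events.
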